### **9.4 Protocol Deviations**

The list of protocol deviations will be compiled prior to database lock. All deviations will be reviewed and decisions for handling each of the deviations will be made prior to the start of data analysis.

### **9.5. Endpoints**

#### **9.5.1. Primary Endpoint**

The time during which 1.0 mL of Spectrum Advanced Hand Sanitizer Gel with Aloe Vera and Vitamin E remains wet under conventional use conditions.

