**CONFIDENTIAL**

# 1. PROTOCOL SUMMARY

## 1.1. Synopsis

**Title:**

Wet Time for a Foam Hand Sanitizer with 70% ethyl alcohol

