**Phase:**

Post-market.

---

\* The study is to include an interim analysis of the data after 46 participants have completed the study on the medium dispenser setting (1.0 mL). If the results demonstrate a satisfactory 15 second wet time using the medium setting, the study will end and no further recruitment will take place. If at this point, the results demonstrate that the amount of hand sanitizer dispensed under the medium setting (1.0 mL) does not sufficiently stay wet for at least 15 seconds, a second data collection will take place with another 46 participants who will undergo the study using the high dispenser setting (1.4 mL).

Primary Objective:	To determine the duration of time during which a 1.0 mL or 1.4 mL* aliquot of Spectrum Advanced Hand Sanitizer Foam remains wet under conventional use conditions.
Primary Endpoint:	The time during which 1.0 mL or 1.4 mL* of Spectrum Advanced Hand Sanitizer Foam remains wet under conventional use conditions.
Study Population:	
Number of participants, N = 46.
 
Inclusion criteria
 
Individuals who meet the following criteria will participate in this study:
 
 
➤ Individual <math>\geq</math> 18 years of age.
 
 
Exclusion criteria
 
Individuals who meet any of the following criteria will not be allowed to participate in this study:
 
 
➤ Individual has a self reported skin condition that might result in irritation from the hand sanitizer.
 
➤ Individual has a known allergy to the ingredients in the test product.
 

Power Analysis Methods:	The sample size of 46 was estimated for 95% confidence interval based on a standard deviation of 5 seconds and target distance from mean to limits of 1.5 seconds (PASS-Confidence Intervals for One Mean). Results from a previous study conducted by Ecolab (summarized in the Appendix) was utilized as a starting point for sample size estimation for the current protocol, using PASS 2021 Power Analysis and Sample Size Software (2021). NCSS, LLC. Kaysville, Utah, USA, ncss.com/software/pass .
Description of Sites/Facilities Enrolling Participants:	
The study will be conducted at private rooms within the Northfield location of Medline Industries, LP.
 
Address: [name]

---

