### **2.2. Study Products**

#### **2.2.1. Medline Spectrum™ Advanced Hand Sanitizer Foam (70%)**

Spectrum Advanced Hand Sanitizer Foam kills over 99.99% of germs within 15 seconds. The formula includes added moisturizers to help reduce dry skin. The SKU number for Medline Spectrum Advanced Hand Sanitizer Foam is HH70F1000H.

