**Figure 1. Hand Sanitizer Application Steps (Adapted from the WHO “How to Handrub?” Poster)**

The participants will then be instructed by study staff to apply a 1.0 mL or 1.4 mL\* aliquot of Spectrum Advanced Foam to their hands, which will be provided from an automated dispenser, following the hand sanitizer application steps. Study staff will begin to measure the wet time using a calibrated stopwatch: the application of the product to the palm of the participant will indicate the “start time”, and the participant stating that their hands have dried will indicate the “stop time”.

Once the participant has indicated that their hands are dry enough to don medical gloves, study staff will stop the stopwatch and record the Spectrum Advanced Foam wet time in the CRF.

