## **9.8. Statistical Analysis**

Statistical analyses will be conducted in SAS® software, Version 9.4 or higher of the SAS System for Windows (Copyright © 2013 SAS Institute Inc.) or other appropriate statistical software.  $P < 0.05$  will be considered statistically significant.

All continuous variables will be summarized using the following descriptive statistics: (non-missing sample size), mean, standard deviation, median, maximum and minimum. The frequency and percentages (based on the non-missing sample size) of observed levels will be reported for all categorical measures. 95% confidence intervals will be calculated for all means.

A box-and-whisker plot will be employed to display the mean, interquartile range, range, and any possible outliers for wet-to-dry time.

Spearman correlation analysis will be used to examine possible associations between the key variable of dry time with age, sex, and hand size. Additional t-tests or non-parametric tests will be employed to further examine any significant associations found in the correlational analyses between key and covariate measures.

If the results of the interim analysis of 46 participants on the medium dispenser setting (1.0 mL) does not demonstrate that hands stay sufficiently stay wet for at an average of at least 15 seconds, a second data collection whereby another 46 participants will undergo the study using the high dispenser setting (1.4 mL) will take place. All analyses presented above would then be repeated for the data from an additional 46 participants at the high dispenser setting (1.4 mL).

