## **12. APPENDIX**

### **a. Hand Sanitizer Product Ingredients**

#### **i. Spectrum™ Advanced Hand Sanitizer Foam**

Ingredients (Active): 70% v/v Ethyl Alcohol

Ingredients (Inactive): (Alphabetical) denatonium benzoate, Glycerin, Glyceryl caprylate, Isopropyl myristate, PEG-12 dimethicone, t-butyl alcohol, Water

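### Does naming a gel in the Section 9.5.1 primary endpoint leave this foam study without a usable endpoint?

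*Combined protocol and SAP*

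**What the plan says.** The primary endpoint is formally stated in three places. Section 9.5.1, within the statistical considerations, reads "The time during which 1.0 mL of Spectrum Advanced Hand Sanitizer Gel with Aloe Vera and Vitamin E remains wet under conventional use conditions". The Primary Endpoint row of the synopsis reads "The time during which 1.0 mL or 1.4 mL* of Spectrum Advanced Hand Sanitizer Foam remains wet under conventional use conditions", and the endpoint column of Section 3 has the same sentence. Section 9.5.2 says that there is no secondary endpoint, so this is the study's only endpoint.

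The rest of the document describes one test product. The title is "Wet Time for a Foam Hand Sanitizer with 70% ethyl alcohol". Section 2.2.1 identifies the product by stock number: "The SKU number for Medline Spectrum Advanced Hand Sanitizer Foam is HH70F1000H". In Section 6.1.2, once the participant declares the hands dry, "study staff will stop the stopwatch and record the Spectrum Advanced Foam wet time in the CRF". Appendix 12.a lists the inactive ingredients as "denatonium benzoate, Glycerin, Glyceryl caprylate, Isopropyl myristate, PEG-12 dimethicone, t-butyl alcohol, Water".

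On the second volume, Section 9.8 says what happens if the 1.0 mL results fall short: "All analyses presented above would then be repeated for the data from an additional 46 participants at the high dispenser setting (1.4 mL".

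**The concern.** Section 9.5.1 is the only endpoint definition inside the statistical section, and read literally it concerns a product that no participant receives. The gel cannot be a second name for the foam, because neither aloe vera nor vitamin E is among the foam's listed ingredients. No sentence says which endpoint statement prevails. Section 9.8 refers to the outcome only as a drying time, without naming a product, so it does not correct 9.5.1.

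Section 9.5.1 also mentions only 1.0 mL, although a second cohort at 1.4 mL may be recruited.

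If the definition were truly ambiguous, the report's conclusion about the 15-second criterion could not be traced to a pre-specified endpoint, and the 1.4 mL cohort would have no stated endpoint in Section 9.

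**Working it through.** **1. The plan's own figure.** Section 9.1 gives a 95% confidence interval for one mean, a standard deviation of 5 s and a target distance from mean to limit of 1.5 s. It arrives at 46 participants. The half-width is t(0.975, n − 1) × 5 / √n, taking the interval as two-sided with the standard deviation estimated from the data.

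- n = 45: 2.0154 × 5 / 6.7082 = 1.502 s, just above the target.
- n = 46: 2.0141 × 5 / 6.7823 = 1.485 s, which meets it.

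The smallest adequate n is 46, as stated. (The normal approximation gives (1.96 × 5 / 1.5)² ≈ 42.7, rounded up to 43, so the plan evidently used the t version.) The inputs are a standard deviation and a precision target. Replacing the word gel with foam alters neither.

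**2. The product, place by place.**

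| Place | Product |
|---|---|
| Title | Foam |
| Synopsis, primary endpoint | Foam |
| Section 2.2.1, study product | Foam, with stock number |
| Section 3, primary endpoint | Foam |
| Section 4.1, design and definition of wet time | Foam |
| Section 6.1.2, application and recording | Foam |
| Appendix 12.a, ingredients | Foam: 1 active and 7 inactive ingredients, no aloe vera or vitamin E |
| Section 9.5.1, primary endpoint | Gel |

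In the text available for review, the gel appears in Section 9.5.1 and nowhere else.

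**3. What an analyst could do with the gel wording.** The dispenser delivers foam, the stopwatch times foam, and the case report form records foam wet time. No gel observation will exist, so the literal reading of 9.5.1 cannot be carried out. The other two endpoint statements give the one reading that can.

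**4. Traceability to 15 seconds.** Section 3 sets the foam endpoint beside its justification, the minimum wet time of 15 s. Section 4.1 repeats that purpose for the foam and gives the start and stop rules for the stopwatch. Sections 8 and 9.8 apply the average of 15 s to the dispenser setting tested. The chain from measurement to conclusion does not need the product name in 9.5.1.

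**5. The volume.** The 1.4 mL setting is a conditional second stage. Naming only the first-stage volume is incomplete but compatible with that design. Section 9.8 repeats all analyses on the additional 46 participants, which is a separate analysis of a separate cohort. No pooled analysis across volumes is described anywhere.

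**The case for a change.** The best argument for acting is that this is the sole primary endpoint, stated wrongly in the one section that governs the analysis, and that a single sentence would cure it. A reader who goes straight to Section 9 meets a different product, and nothing in that section puts the reader right. An endpoint definition should not depend on the reader's good sense. It can also be said that the Section 3 wording, with its two volumes joined by an alternative, does not itself say that each cohort is evaluated on its own.

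The factual part of this stands. The sentence is current Version 4.0 text and is wrong about the product, and there is no sign of redaction or damaged extraction. The consequence does not stand. A contradiction in an endpoint matters when two readings could lead to different data, analyses or conclusions, and here only one reading is possible. Separate evaluation by volume is already supplied by Section 9.8, so further wording would be a matter of taste. Anyone who reopens the document for another reason may align 9.5.1 with Section 3, but that is proofreading.

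**Conclusion.** Section 9.5.1 contains an isolated naming error: one of three formal endpoint statements names the wrong product. The likely explanation is text carried over from a protocol for another product, though the documents do not say so and the conclusion does not depend on it. The error changes no procedure, recorded variable, analysis method or decision rule, and the sample size stays at 46 per dispenser setting (half-width 1.485 s against the 1.5 s target). The missing 1.4 mL wording is an incompleteness that Section 9.8 covers. No change to the plan is needed.

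This rests on two assumptions: that the study was run with the product identified in Section 2.2.1, and that the report takes the foam endpoint from Section 3 and the synopsis. The pages withheld from review could mention the gel, but that would not alter which product is dispensed and timed under Section 6.1.2.

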#### **9.5.2. Secondary Endpoint**

None.

### **9.6. Demographics, Variables and Covariates**

Age will be collected as a continuous measure, with all participants being  $\geq 18$  years of age. Age strata will be defined as stratum 1: 18-25 years old, stratum 2: 26-41 years old, stratum 3: 42-57 years old, stratum 4: 58-67 years old, stratum 5: 68-76 years old, stratum 6: 77-94 years old, 95+ years old. Age will be considered for secondary analysis.

Sex will be collected as a categorical equal to 0=male, 1=female, or 2=other. Sex will be considered for secondary analysis.

Hand size will be calculated using the formula  $2.48 \times \text{hand length} \times \text{hand breadth}$  as described by (Wilkinson et al. (2017), Bellissimo-Rodrigues et al. (2015) and Hsu and Yu (2010)).

## **9.7. Handling of Missing Values**

All missing data will be quantified in the final report and possible biases for any missing data will be reported.

## **9.8. Statistical Analysis**

Statistical analyses will be conducted in SAS® software, Version 9.4 or higher of the SAS System for Windows (Copyright © 2013 SAS Institute Inc.) or other appropriate statistical software.  $P < 0.05$  will be considered statistically significant.

All continuous variables will be summarized using the following descriptive statistics: (non-missing sample size), mean, standard deviation, median, maximum and minimum. The frequency and percentages (based on the non-missing sample size) of observed levels will be reported for all categorical measures. 95% confidence intervals will be calculated for all means.

A box-and-whisker plot will be employed to display the mean, interquartile range, range, and any possible outliers for wet-to-dry time.

Spearman correlation analysis will be used to examine possible associations between the key variable of dry time with age, sex, and hand size. Additional t-tests or non-parametric tests will be employed to further examine any significant associations found in the correlational analyses between key and covariate measures.

If the results of the interim analysis of 46 participants on the medium dispenser setting (1.0 mL) does not demonstrate that hands stay sufficiently stay wet for at an average of at least 15 seconds, a second data collection whereby another 46 participants will undergo the study using the high dispenser setting (1.4 mL) will take place. All analyses presented above would then be repeated for the data from an additional 46 participants at the high dispenser setting (1.4 mL).

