### **5. STUDY POPULATION**

#### **5.1. Inclusion Criteria**

Individuals who meet the following criteria will participate in this study:

- Individual  $\geq$  18 years of age.

---

\* The study is to include an interim analysis of the data after 46 participants have completed the study on the medium dispenser setting (1.0 mL). If the results demonstrate a satisfactory 15 second wet time using the medium setting, the study will end and no further recruitment will take place. If at this point, the results demonstrate that the amount of hand sanitizer dispensed under the medium setting (1.0 mL) does not sufficiently stay wet for at least 15 seconds, a

*second data collection will take place with another 46 participants who will undergo the study using the high dispenser setting (1.4 mL).*

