## **9. STATISTICAL CONSIDERATIONS**

### **9.1. Sample Size Determination**

The sample size of 46 was estimated for 95% confidence interval based on a standard deviation of 5 seconds and target distance from mean to limits of 1.5 seconds (PASS-Confidence Intervals for One Mean). Results from a previous study conducted by Ecolab (summarized in the Appendix) was utilized as a starting point sample size estimation for the current protocol, using PASS 2021 Power Analysis and Sample Size Software (2021). NCSS, LLC. Kaysville, Utah, USA, [ncss.com/software/pass](http://ncss.com/software/pass). In the event that a participant withdraws from the study, additional participants will be enrolled to achieve a final number of 46 participants with complete data and until adequate power for analysis has been reached.

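### Minor, secondary analysis only: sex has three unordered codes but is tested by Spearman correlation, so anyone coded 'other' makes the result depend on an arbitrary order

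*Combined protocol and SAP*

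**What the plan says.** Section 9.6 defines the variable: "Sex will be collected as a categorical equal to 0=male, 1=female, or 2=other". It also fixes its role: "Sex will be considered for secondary analysis".

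Section 9.8 gives the method: "Spearman correlation analysis will be used to examine possible associations between the key variable of dry time with age, sex, and hand size". Group comparisons come second and are conditional: "Additional t-tests or non-parametric tests will be employed to further examine any significant associations found in the correlational analyses". A p-value below 0.05 "will be considered statistically significant"; whether tests are one- or two-sided is not stated.

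No section says that code 2 will be excluded, merged with another group, or analysed by a method for unordered groups. The eligibility criteria in Sections 5.1 and 5.2 place no restriction on sex. If the 1.4 mL stage is run, Section 9.8 repeats the same analyses on a further 46 participants.

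**The concern.** Spearman correlation replaces each code by its rank. For age and hand size the order is real. For sex it comes only from the numeric labels: 'other' stands above female, and female stands between male and 'other'. With two groups this does no harm, because swapping the labels only changes the sign of the coefficient. With three groups, relabelling can change both the coefficient and its p-value.

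The conditional follow-up makes this worse. The group tests suited to a nominal variable run only if the order-dependent correlation is significant. A male-female difference missed at the first step is not recovered later in the plan. At stake is the sex finding in a secondary analysis and nothing more.

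**Working it through.** **Inputs from the plan.** N = 46 and SD 5 s (Section 9.1), significance at 0.05 (Section 9.8, taken as two-sided), three sex codes (Section 9.6).

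**Assumed, because the plan gives no figure.** The male-female difference (1.5, 3 or 4.5 s), the number k coded 'other' (0, 1 or 2), where their wet times lie (like males, midway, like females), near-equal numbers of men and women, and normal wet times.

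**Step 1: the plan's own figure.** Section 9.1 sizes the study for a 95% confidence interval "based on a standard deviation of 5 seconds and target distance from mean to limits of 1.5 seconds". The smallest n with t(0.975, n−1) × 5/√n ≤ 1.5 is 46:
- n = 45: 2.015 × 5/√45 = 1.502 s
- n = 46: 2.014 × 5/√46 = 1.485 s

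N = 46 is reproduced and is not in dispute. It was not derived for a comparison by sex.

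**Step 2: does the order matter?** Take 46 distinct wet times, with 22 men and 21 women alternating in ranks 1 to 43 and three 'other' participants holding the three longest times.
- Plan's codes (0, 1, 2): rho = 0.205, p = 0.17
- 'Other' placed between male and female: rho = 0.005, p = 0.97
- Kruskal-Wallis, which ignores order: p = 0.016

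In 2,000 simulated trials per scenario, the three possible orderings were compared with 'other' distributed like males. With one 'other', the verdict at 0.05 changed with the ordering in about 6% of trials when there was no sex difference and about 21% when the difference was 3 s. With nobody coded 2 it never changed.

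**Step 3: power.** There were 20,000 replicates per scenario, with the remaining 46 − k split as evenly as possible between men and women. Each cell shows Spearman under the plan's codes / rank-sum for male against female, in percent.

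| Difference | k | 'Other' like males | Midway | Like females |
|---|---|---|---|---|
| 4.5 s | 1 | 74.4 / 81.8 | 78.4 / 81.4 | 82.7 / 82.3 |
| 4.5 s | 2 | 64.1 / 80.8 | 73.1 / 80.7 | 80.9 / 80.6 |
| 3 s | 1 | 41.4 / 47.9 | 44.5 / 47.3 | 48.5 / 48.3 |
| 3 s | 2 | 34.9 / 47.4 | 41.3 / 47.4 | 47.9 / 47.9 |
| 1.5 s | 1 | 14.6 / 15.8 | 15.0 / 15.6 | 15.9 / 15.5 |
| 1.5 s | 2 | 12.4 / 15.6 | 14.2 / 15.8 | 15.6 / 15.1 |

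With k = 0 the two methods gave the same verdict in every replicate: 83.1% at 4.5 s, 49.6% at 3 s and 16.2% at 1.5 s. With no true difference Spearman rejected in 4.8% to 4.9%, so type I error is not inflated.

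**Step 4: how often it would arise.** If each participant has probability p of being coded 2, the chance of at least one among 46 is 1 − (1 − p)^46. For assumed p of 0.5%, 1% and 2% this is 21%, 37% and 61%.

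The average power loss is P(k=1) × loss₁ + P(k=2) × loss₂. At 4.5 s with 'other' midway, the losses are 3.04 and 7.59 points:
- p = 0.5%: 0.184 × 3.04 + 0.021 × 7.59 = 0.7 points
- p = 1%: 0.293 × 3.04 + 0.067 × 7.59 = 1.4 points
- p = 2%: 0.371 × 3.04 + 0.170 × 7.59 = 2.4 points

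Three or more 'other' participants are ignored (probability 0.2%, 1.1% and 6.4%).

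**The case against.** The case for leaving the plan alone is that the problem may never occur and is small on average. At the assumed rates, code 2 stays empty in 79%, 63% or 39% of studies. A 4.5 s difference is 0.9 SD and three times the plan's 1.5 s precision target. Using the midway powers above, the average loss is about 0.6, 1.2 and 2.1 points at 3 s, and 0.1, 0.3 and 0.5 points at 1.5 s. The large losses need the 'other' participants to resemble males; if they resemble females the methods have equal power within simulation error. Section 9.5.2 lists no secondary endpoint, and no decision uses the sex result. Section 9.8 also tabulates each observed level, so readers would see whether code 2 occurred.

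All of this stands, and it is why the point is minor. It does not remove the error: the plan provides for a third category and gives it a test that depends on label order.

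On the remedy, excluding 'other' from the sex test sits awkwardly with Section 9.3, which analyses everyone with full data. Kruskal-Wallis would keep all three groups, though it spends a second degree of freedom on a group of perhaps one or two. A lighter repair is to leave code 2 out of the sex correlation and describe it, which gives the same sex verdict as the rank-sum test. Either is defensible if stated in advance.

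**Conclusion.** The concern holds and is minor. As written, Sections 9.6 and 9.8 apply an ordinal method to a nominal variable with three levels. The effect is nil if code 2 is empty. With one or two 'other' participants, power for a male-female difference ranges from unchanged to a loss of about 17 points (64.1% against 80.8%: two 'other' like males, 4.5 s). On average the loss is about 0.7 to 2.4 points at 4.5 s. At 1.5 s power is about 16% or less by either method, so the sex check is weak with or without the change.

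These sizes rest on assumed differences, numbers and locations of 'other', and rates of code 2; only N and the SD come from the plan. The ordering problem itself needs no assumption beyond at least one participant coded 2.

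**What to change.** In Section 9.8, restrict Spearman correlation to age and hand size. State that wet time will be compared between male and female participants by a Wilcoxon rank-sum test, performed whatever the correlations show, and that wet times of participants coded 'other' will be reported descriptively. Apply the same wording to the 1.4 mL data if that stage is run.

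The cost is one or two sentences and no new data. If nobody is coded 2, the verdict at 0.05 is the one Spearman would have given: it agreed in every simulated trial, with p-values differing by at most 0.006. The drawback is that 'other' participants do not contribute to the sex test; they remain in the overall mean and its confidence interval.

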#### **6.1.1.2. Verification and Eligibility**

The PI or delegated study staff will verify the eligibility of the individual for the study, based on the inclusion and exclusion criteria that will be evaluated in the Participant Screening Form. Participant demographics (age and sex), as well as hand size, will be documented. Study staff will verify participant eligibility in the study in-person or over a video conference call with the

participant. The participant will receive a unique screening number that will be recorded in the Participant Screening Form. The participant responses will be included in the Participant Screening Form.

Successfully enrolled participants will be assigned a unique participant identification number based on the order in which they enroll. If the individual is considered eligible to participate in the study, the participant will proceed to the study activities detailed in section 6.1.2.

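### Section 9.8 relates wet time to age, sex and hand size one at a time, so a sex association could not be told apart from a hand-size effect and no estimate in seconds by hand size is prespecified

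*Combined protocol and SAP*

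**What the plan says.** Section 6.1.1.2 provides that "Participant demographics (age and sex), as well as hand size, will be documented". Section 9.6 defines hand size as a continuous area computed from hand length and breadth, sets strata for age but none for hand size, and codes sex 0, 1 or 2. Of sex it says: "Sex will be considered for secondary analysis".

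Section 9.8 gives the association analysis: "Spearman correlation analysis will be used to examine possible associations between the key variable of dry time with age, sex, and hand size". It continues: "Additional t-tests or non-parametric tests will be employed to further examine any significant associations found in the correlational analyses between key and covariate measures". A P value below 0.05 "will be considered statistically significant", and "95% confidence intervals will be calculated for all means". Neither section names a regression, a partial correlation or any other analysis that uses the three covariates together.

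The 15 s criterion is applied to the average over all participants (sections 8 and 9.8). Section 9.5.2 lists no secondary endpoint.

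**The concern.** Every participant at a given setting receives the same volume. A larger hand spreads it more thinly, so hand area is a plausible determinant of wet time. If men in the sample tend to have larger hands, a separate test on sex picks up part of the hand-size effect. The report could then present sex as a factor in its own right with no prespecified result to check this against.

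A Spearman coefficient also has no units. It cannot say how many seconds are lost on a large hand, or where mean wet time for large hands lies relative to 15 s. What is at stake is how the covariate results are read, not the primary result.

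A smaller point: Spearman correlation treats sex codes 0/1/2 as ordered, which has no meaning if any participant is coded 2.

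**Working it through.** **The plan's own figure.** Section 9.1 says "The sample size of 46 was estimated for 95% confidence interval", with a "standard deviation of 5 seconds and target distance from mean to limits of 1.5 seconds". The smallest n with t(0.975, n−1) × 5/√n ≤ 1.5 is 46 (half-width 1.485 s; n = 45 gives 1.502 s). So 46 reproduces. It was chosen for the precision of one mean, not for covariate analysis.

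**Inputs.** From the documents: n = 46, SD 5 s, 0.05 level (taken as two-sided). Assumed, because the documents give no figure: half men; overall mean 17 s (close to the 17.1 s in the appendix study of another product); men's hand area 10% to 25% larger; within-sex CV of area 9%; wet time proportional to area to the power −0.5 or −1; no direct effect of sex.

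**Implied correlation of sex with area.** With women's mean area set to 1 and an area ratio of 1.20:
- half the sex difference = 0.10
- within-sex variance = (0.09² + 0.108²)/2 = 0.00988
- r = 0.10/√(0.10² + 0.00988) = 0.71

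The same formula gives 0.47 at ratio 1.10 and 0.78 at 1.25.

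**Implied correlation of area with wet time.** To first order this is −exponent × CV of area × 17/5. At ratio 1.20 the overall CV is 0.141/1.10 = 0.128, giving −0.44 for inverse proportionality and −0.22 for exponent 0.5.

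**Closed-form check on the sex test.** The induced correlation of sex with wet time has size about 0.71 × 0.44 = 0.31. On the Fisher scale, atanh(0.31) × √43 = 2.10, so the chance of exceeding 1.96 is about 56%.

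**Simulation (4,000 trials per scenario), share with a significant Spearman test on sex:**

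| Area ratio, men/women | 1.10 | 1.15 | 1.20 | 1.25 |
|---|---|---|---|---|
| Exponent 0.5 | 8% | 12% | 17% | 24% |
| Exponent 1 | 19% | 35% | 55% | 77% |

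In a linear model that also contains hand area, the sex term is significant in 4% to 6%. Setting the correlations directly instead (sex with hand size 0.5 to 0.8, hand size with wet time −0.3 to −0.6) gives 18% to 94% marginally and 4% to 6% adjusted.

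**What the overall mean can conceal.** At ratio 1.20 with inverse proportionality, women average 17 × 2/(1 + 1/1.2) = 18.5 s and men 18.5/1.2 = 15.5 s. Across the four ratios, the true mean at the 90th-percentile hand area is 13.9 to 14.9 s with exponent 1 and 15.4 to 15.9 s with exponent 0.5.

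**How often the follow-up tests would run.** With n = 46, 80% power needs a correlation of tanh((1.960 + 0.842)/√43) = 0.40. With exponent 0.5, Spearman on hand size is significant in only 19% to 36% of trials, so the conditional tests on hand size would usually not be triggered.

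**Precision of a prediction by hand size.** For a hand size–wet time correlation of −0.5, the residual SD is 5 × √0.75 = 4.33 s. The half-width at the 90th percentile is then about 2.015 × 4.33 × √(1/46 + 1.28²/45) = 2.1 s. It is about 2.2 to 2.5 s in the area scenarios.

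**The case against.** The strongest reply has four parts.

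- **The plan goes beyond Spearman.** With follow-up t-tests and intervals for all means, a significant sex correlation could lead to group means in seconds. This stands: a reader might infer that the plan yields nothing in seconds on covariates, and that would be wrong. What remains is narrower. The follow-ups are conditional, define no hand-size groups, are not compared with 15 s, and a t-test on sex repeats the same unadjusted contrast.
- **The 8% to 77% is not an error rate.** This also stands. In the simulated population men do have shorter wet times, so a marginal test that detects this is correct. Section 9.8 promises only to examine associations. The difficulty is one of interpretation: the planned analysis cannot say whether the association remains at a given hand size.
- **The question is secondary.** True. No objective or decision rule concerns people with large hands, and 15 s is applied to the overall average.
- **Adjustment is weak at n = 46.** True. At ratio 1.20 with inverse proportionality, power for hand size falls from about 86% to 59% once sex and age are in the model. With exponent 0.5 it is only about 15% to 18%. This argues for an exploratory label, and for taking predictions by hand size from a model without sex.

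**Conclusion.** The point holds as a cheap improvement to a secondary analysis. The planned tests take one factor at a time, so they cannot separate sex from hand size, and no output shows wet time in seconds by hand size beside 15 s.

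The size depends on assumptions that the documents can neither confirm nor exclude. At the weak end the sex test is significant in 8% of trials, barely above the nominal 5%; at the strong end, in 77%.

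Two stronger readings are tempting and unsupported. One is that sex and hand size are known to be strongly linked here: the documents say nothing about the link. The other is that large-handed users will fall below 15 s: in these scenarios that depends on the assumed exponent. The primary mean, its interval, N = 46 and the choice of whether to proceed to 1.4 mL do not change.

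**What to change.** Add one paragraph to section 9.8, labelled exploratory:

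1. Fit a linear regression of wet time on continuous hand size. Report the slope in seconds per stated unit of hand area, and the predicted mean wet time with 95% CI at the 10th, 50th and 90th percentiles of observed hand size, beside 15 s. Check linearity, for example by refitting with log hand size.
2. Fit a second model that adds sex and continuous age. Report each coefficient in seconds with its 95% CI. Enter sex as a categorical factor, because its codes are nominal.
3. Keep the Spearman coefficients as descriptive only.

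If the 1.4 mL stage takes place, these models are repeated with the other analyses, as 9.8 already provides.

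The cost is one paragraph and two models on data already collected, with no added participants or procedures. The downside is imprecision: adding sex widens the hand-size interval (variance inflation about 1/(1 − 0.71²) = 2.0 at ratio 1.20), and the 90th-percentile prediction carries a half-width of about 2.2 to 2.5 s. The text should say that a wide interval spanning 15 s settles nothing for large hands.
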